## 2.4 Determination of sample size

Up to 45 subjects are anticipated to enroll in PS0018. This number is based on the fact that 45 subjects are planned to be randomized in the feeder study, PS0016. The calculations to reach that sample size are outlined in the PS0016 protocol. As the primary objective of the PS0018 study is to assess the long-term safety and tolerability of bimekizumab 160mg Q4W, the number of subjects anticipated is based on the number of subjects completing PS0016 and meeting eligibility requirements for PS0018.

# 3 DATA ANALYSIS CONSIDERATIONS

## 3.1 General presentation of summaries and analyses

Statistical evaluation will be performed by PAREXEL. The datasets will follow the UCB analysis data model (ADaM) data specifications.

All analyses will be performed using SAS version 9.3 or higher (SAS Institute, Cary, North Carolina, United States).

Continuous variables will be summarized by PS0016 randomized treatment group, visit and timepoint (where applicable) including number of subjects (n), mean, standard deviation (SD), median, minimum, maximum and confidence intervals (CI) where stated in the SAP. Categorical variables will be summarized by PS0016 randomized treatment group, visit and timepoint (where applicable) with frequency counts and percentages. Coefficient of variation (CV), geometric mean and 95% CI for the geometric mean will also be presented in the descriptive statistics for

the PK concentration data. In all outputs the confidence limits will be restricted to the possible values that the variable can take.

When reporting relative frequencies or other percentage values, the following rules apply:

- For values where all subjects fulfill certain criteria, the percentage value will be displayed as 100
- For values where the absolute frequency is zero, there will be no percentage displayed at all
- All other percentage displays will use 1 decimal place
- Percentages displayed based on continuous data (eg percentage changes from baseline) will be displayed to 1 decimal place. Unless otherwise stated, the denominator for the percentages will be based on the number of subjects in the respective analysis.
- When reporting descriptive statistics, the following rules will apply in general (with the exception of PK concentration data, for which additional rules are stated below):
  - n will be an integer
  - Mean (arithmetic and geometric), SD and median will use 1 decimal place more than the original data
  - CV will be reported as a percentage to 1 decimal place
  - Minimum and maximum will be reported using the same number of decimal places as the original value
  - If no subjects have data at a given timepoint, for example, then only n=0 will be presented. If n<3, then only the n, minimum and maximum will be presented. If n=3, then only n, median, minimum and maximum will be presented. The other descriptive statistics will be left blank

When reporting individual values and descriptive statistics for PK concentration data, the following rules will apply with regard to rounding and precision:

- Individual values for PK concentration data will be reported to the same level of precision as received from the bioanalytical laboratory
- Descriptive statistics for PK concentration data will be reported to the same level of precision as the individual data for the minimum and maximum, and to 1 additional significant figure for the mean (arithmetic and geometric), median, SD and 95% CI for the geometric mean
- Geometric CV (geoCV) will be reported as a percentage to 1 decimal place

All tabulations will be presented by treatment group, visit and timepoint (where applicable). In the tabulations, the order the treatment groups will be displayed is detailed in [Section 3.6](#).

Data listings containing all documented data and all derived data will be generated. Data listings will highlight the dose switching; all timepoints on or after the dose increases to 320mg Q4W will be flagged, up to the time point the dose switches back to 160mg Q4W.

## 3.2 General study level definitions

### 3.2.1 Analysis time points

#### 3.2.1.1 Relative day

Relative day for an event will be derived with the date of the first sc injection of investigational medicinal product (IMP) in PS0018 as reference.

Relative days for an event of measurement occurring before the date of first sc injection are calculated as follows:

$$\text{Relative Day} = \text{Event Date} - \text{Date of First Injection in PS0018} \quad [1]$$

The relative day for an event or measurement occurring on or after the reference date to the date of the last injection is calculated as follows:

$$\text{Relative Day} = (\text{Event Date} - \text{Date of First Injection in PS0018}) + 1 \quad [2]$$

For events or measurements occurring after the date of the last injection, relative day will be prefixed with '+' in the data listings and will be calculated as follows:

$$\text{Relative Day} = \text{Event Date} - \text{Date of Last Injection in PS0018} \quad [3]$$

There is no relative Day 0. Relative day is not calculated for partial dates in cases where relative day is shown in a subject data listing. In such cases, relative day should be presented as '-' in the subject data listings.

For AE listings only, relative day will, in addition, be calculated with respect to the first sc injection in PS0016.

#### 3.2.1.2 Study periods

For each subject, the study duration is estimated to be up to a maximum of 64 weeks:

- Open-Label Treatment Period: 48 weeks
- SFU Visit: 20 weeks after the last dose of study medication scheduled at Week 44

The end of the study is defined as the date of the last visit of the last subject in the study.

### 3.2.2 Daylight saving dates

Daylight saving dates will be considered in the calculation of the absolute scheduled and actual times and in the duration when this is based on times. Therefore, if any daylight saving change occurs during the study development, this will impact the description of the blood sample collections, the calculation of the PK parameters, and any AE duration in case the time is included in the calculation of the duration.

## 3.3 Definition of Baseline values

Baseline is defined as the last available value prior to the first injection of study medication in the PS0016 study.

All changes from Baseline refer to changes from PS0016 Baseline, unless stated otherwise. Scheduled or unscheduled measurements can be used as the Baseline value in either case. Measurement specific Baseline timepoints are presented in [Table 3-1](#).

**Table 3–1: Definition of Baseline**

Category	Measurement or analysis	Definition of Baseline
Safety	Clinical laboratory values (chemistry, hematology, and urinalysis) Vital signs 12-lead ECG results	PS0016 Baseline Visit or if missing the PS0016 Screening results.
Safety	C-SSRS	The ‘Baseline’ version of the questionnaire will be completed at PS0016 Screening and the ‘Since Last Visit’ version will be completed at all subsequent visits.
Efficacy	PASI score IGA score BSA affected by psoriasis HADS	PS0016 Baseline Visit or if missing the PS0016 Screening results
Immunological	ADA	PS0016 Baseline

ADA=anti-drug (bimekizumab) antibody; BSA=body surface area; C-SSRS = Columbia-Suicide Severity Rating Scale; ECG=electrocardiogram; HADS=Hospital Anxiety and Depression Scale; IGA=Investigator’s Global Assessment; PASI=Psoriasis Area and Severity Index.

If a measurement is repeated at the defined Baseline and is obtained prior to receiving the first dose of study medication, then the last available measurement will be used as the Baseline value.

The rollover visit from PS0016 will be the entry visit into PS0018. The day of first dose will be labelled as PS0018 Week 0 in the tabulations, and will be included in any change from PS0016 Baseline summaries.

### 3.4 Protocol deviations

Important protocol deviations are deviations from the protocol which potentially could have a meaningful impact on study conduct or on the key safety, efficacy or PK outcomes for an individual subject. The criteria for identifying such protocol deviations will be defined within the protocol deviation specifications document which is part of the data cleaning plan. Important protocol deviations will include the following categories:

- Inclusion criteria deviation
- Exclusion criteria deviation
- Withdrawal criteria deviation
- Prohibited concomitant medication use
- Incorrect treatment or dose
- Treatment non-compliance
- Procedural non-compliance

Important protocol deviations will be reviewed as part of the ongoing data cleaning process and data evaluation.

After all data have been verified/coded/entered into the database, the final data evaluation meeting (DEM) will be performed. The purpose of this DEM will be to review all protocol deviations, define the analysis sets and check the quality of the data prior to database lock. The review will also help decide how to manage problems in the subjects' data (eg missing values and withdrawals).

After the pre-analysis review, resolution of all issues, and documentation of all decisions, the database will be locked.

### **3.5 Analysis sets**

#### **3.5.1 Enrolled Set**

The Enrolled Set (ES) will consist of all subjects who have given informed consent for PS0018. This is equivalent to All Subjects Screened.

#### **3.5.2 Safety Set**

The Safety Set (SS) will consist of all subjects who received at least 1 dose of the study medication in PS0018.

Safety variables will be summarized on the SS.

#### **3.5.3 Full Analysis Set**

The Full Analysis Set (FAS) will consist of all enrolled subjects who received at least 1 dose of the study medication and have a valid efficacy measurement for PASI at PS0018 Week 0.

Efficacy variables will be summarized based on the FAS.

#### **3.5.4 Pharmacokinetic-Per Protocol Set**

The Pharmacokinetic-Per Protocol Set (PK-PPS) will consist of all enrolled subjects who received at least one dose of the study medication, provide at least one quantifiable plasma concentration postdose in PS0018, and have no important protocol deviations that impact the pharmacokinetics.

Pharmacokinetic and immunology variables will be summarized on the PK-PPS.

### **3.6 Treatment assignment and treatment groups**

Treatment assignment for the SS and PK-PPS will be according to the actual treatment received in PS0018, unless stated otherwise in [Table 3–1](#). Analyses of efficacy data (based on the FAS) will be conducted according to the PS0016 randomized treatment group.

Subjects receiving the incorrect treatment (for example due to a dosing error) at a particular visit will be excluded from the PK-PPS as this would be considered as an important protocol deviation. Subjects may be excluded from the analysis at a particular visit (or visits) only, following discussion at the DEM.

Listings will be presented by subjects as randomized in PS0016. Summaries will be presented by treatment group and overall where applicable. See [Table 3–1](#) for the treatment assignment of the 3 different sets of treatment groups.

---

In the TFLs the treatment groups based on the PS0016 randomized treatment group will be displayed as follows, where BKZ refers to bimekizumab and PBO refers to placebo:

- BKZ 320mg + PBO
- BKZ 320mg
- All Subjects

In the TFLs the treatment groups based on the actual PS0018 treatment received (ie PS0018 dose at onset of event or measurement) will be displayed as follows:

- BKZ 160mg Q4W
- BKZ 320mg Q4W
- All BKZ

Lastly there will be the grouping based on dose adjustment in PS0018 defined as follows:

- Nonadjusters – This group consists of subjects who do not experience a dose adjustment during the study.
- Single adjusters – This group consists of subjects who experience just one dose adjustment during the study. Per the protocol, if just a single adjustment occurs, then that adjustment must go from bimekizumab 160mg Q4W to 320mg Q4W.
- Multiple adjusters – This group consists of subjects who experience more than 1 dose adjustment during the study. This means that the subjects in this group dose adjust from bimekizumab 160mg Q4W to 320mg Q4W and then adjust back to 160mg Q4W (with further dose adjustments possible).

For summary purposes, the single and multiple adjuster groupings will be combined.

The treatment group labels and tabulation requirements for each data type are displayed in [Table 3–1](#) **Error! Reference source not found.**

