## 5 STUDY DESIGN

### 5.1 Study description

PS0018 is a multicenter, 48-week, open-label extension study to assess the long-term safety, tolerability, and efficacy of bimekizumab in eligible adult subjects with moderate to severe chronic plaque psoriasis who participated in PS0016.

During the Open-Label Treatment Period, subjects will attend study visits at the site Q4W for study assessments and administration of bimekizumab by study site staff through Week 48. Following completion or early withdrawal from the 48-week Open-Label Treatment Period, subjects will return for a SFU Visit 20 weeks after their last dose of bimekizumab. Subjects withdrawing early from the study will undergo the Early Withdrawal Visit assessments and will enter the SFU Period.

Bimekizumab will initially be administered at a dose of 160mg Q4W subcutaneously (sc) during the 48 week Open Label Treatment Period. There will be an option to increase the dose to 320mg Q4W at the discretion of the Investigator if the subject's PASI response is  $\geq 50\%$  to  $< 75\%$  reduction from the Baseline of PS0016 at Week 12 or later. If the subject's disease is adequately controlled on the 320mg Q4W dose, they may return to 160mg Q4W at the discretion of the Investigator. The decision to return to 160mg Q4W dosing should be based upon treatment response, tolerability, and Investigator discretion, with the aim to use the dosing regimen that achieves the optimal benefit-risk for each subject. If a subject does not achieve a PASI50 at Week 12 or later then they will be withdrawn from the study.

A schedule of study assessments is presented in [Table 5–1](#).

---

A study schematic diagram of PS0018 is presented in [Figure 5–1](#).

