m Bimekizumab will initially be administered at a dose of 160mg Q4W subcutaneously (sc) during the 48 week Open Label Treatment Period. There will be an option to increase the dose to 320mg Q4W at the discretion of the Investigator if the subject’s PASI response is ≥50% to <75% reduction from the Baseline of PS0016 at Week 12 or later. If the subject’s disease is adequately controlled on the 320mg Q4W dose, they may return to 160mg Q4W at the discretion of the Investigator. The decision to return to 160mg Q4W dosing should be based upon treatment response, tolerability, and Investigator discretion, with the aim to use the dosing regimen that achieves the optimal benefit-risk for each subject. If a subject does not achieve a PASI50 at Week 12 or later then they will be withdrawn from the study.

n Subjects should not receive their first dose in PS0018 until at least 4 weeks (+/-3 days) after their last dose in PS0016.

[figure not shown]

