### **7.2 Treatments to be administered**

During the Treatment Period, all subjects will receive bimekizumab 160mg Q4W sc administered for up to 48 weeks in an open-label manner. Subjects should not receive their first dose in PS0018 until at least 4 weeks (+/-3 days) after their last dose in PS0016. At the discretion of the Investigator, and if the subject does not achieve a PASI75 response (75% reduction in the PASI score from the Baseline of PS0016) at Week 12, the bimekizumab dose in PS0018 may be increased to 320mg Q4W sc. If the subject's disease is adequately controlled on the 320mg Q4W dose, they may return to 160mg Q4W. The decision to return to 160mg Q4W dosing should be based upon treatment response, tolerability, and Investigator discretion, with the aim to use the dosing regimen that achieves the optimal benefit-risk for each subject.

The study medication is to be administered in the clinic by study site staff as 1 sc injection for the 160mg dose or 2 sc injections for the 320mg dose. Suitable areas for sc injections are the lateral abdominal wall and upper outer thigh. Injection sites should be rotated and injections should not be given into areas where the skin is tender, bruised, red, or hard.

The minimum time between doses should be no less than 24 days and no more than 32 days for Q4W dosing.

An IMP Handling Manual will be provided to each site containing instructions regarding drug preparation and dosing.

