### **14.5 Planned efficacy analyses**

Efficacy variables will be summarized based on the FAS. The summaries described in this section will provide data on maintenance of effect of open-label bimekizumab over 48 weeks. Additionally, it will allow an assessment of the impact of dose adjustments on efficacy results.

Responder efficacy variables (PASI50, PASI75, PASI90, PASI100, IGA score of 0 or 1, and HADS normal scores) will be summarized descriptively using counts and percentages by scheduled visit and PS0016 randomized treatment group and overall. The PASI responder variables are derived relative to the PS0016 Baseline. Missing data will be handled by using nonresponder imputation (NRI), meaning that subjects that discontinue early or who have missing data at a given time point are imputed as though they did not achieve the given response. Supportive summaries will be based on observed case data.

Continuous efficacy variables based on the change from Baseline (PASI, BSA, and HADS) will be summarized using descriptive statistics by scheduled visit and PS0016 randomized treatment group and overall. The table presentations will display descriptive statistics for the PS0016 Baseline and the observed and change from PS0016 Baseline results by scheduled visit for PS0018. Figures for selected variables will also be generated in order to demonstrate the kinetics of response over time. Missing data will be handled by using multiple imputation (MI) via the

Markov-Chain Monte Carlo (MCMC) method. Supportive summaries will be based on observed case data.

In addition to the summaries described above, the impact of dose adjustment on efficacy will be considered. This will be done primarily by summarizing efficacy variables by the 3 adjuster groups as defined in [Section 14.2.2](#). Furthermore, a supportive analysis specifically for single adjusters will be performed in which PASI score will be summarized by visit, where Baseline is recalibrated for each individual subject and defined as the visit where the bimekizumab 320mg Q4W dose is initiated. The visits summarized will be in weeks relative to when the 320mg Q4W dose was started as opposed to the scheduled week of the PS0018 assessment. These summaries will be based on observed data only.

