## 8.2 Statistical analysis of the primary efficacy variables

In addition to the summaries described below, the impact of dose adjustment on efficacy will be considered. This will be done primarily by using descriptive statistics to summarize PASI score for each visit by PS0016 randomized treatment group and the dose adjustment categories as defined in [Section 4.10](#) along with the All Subjects (ie All BKZ) group. This will be based on observed data only.

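### The adjuster versus nonadjuster PASI tables group subjects by their own post-baseline PASI, so they are confounded by response and cannot show the impact of dose adjustment

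*SAP*

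**What the plan says.** All subjects start on 160mg Q4W. Protocol 5.1 then says: "There will be an option to increase the dose to 320mg Q4W at the discretion of the Investigator". The condition, as worded in the dosing footnote to Protocol Table 5–1, is "PASI response is ≥50% to <75% reduction from the Baseline of PS0016 at Week 12 or later"; Protocol 5.1 and SAP 2.3 carry the same band. Protocol 7.2 words it differently: the increase is open "if the subject does not achieve a PASI75 response" at Week 12, with no lower bound. Subjects below PASI50 at Week 12 or later are withdrawn (Protocol 5.1 and 6.3, SAP 4.2).

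SAP 3.6 defines nonadjusters thus: "This group consists of subjects who do not experience a dose adjustment during the study". Single and multiple adjusters are combined for summaries.

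On the impact of dose adjustment on efficacy, SAP 8.2 says: "This will be done primarily by using descriptive statistics to summarize PASI score for each visit", split by PS0016 arm and adjustment category. It adds: "This will be based on observed data only". SAP 8.2.1 extends the grouping to PASI change (LOCF and observed cases) and to PASI50/75/90/100 (NRI and observed cases), with responder plots. Protocol 14.5 says of its efficacy summaries that "it will allow an assessment of the impact of dose adjustments on efficacy results". There is no randomization to dose (Protocol 7.10) and no covariate adjustment (SAP 4.1).

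**The concern.** Under either wording of the increase criterion, every adjuster has been below PASI75 at some visit from Week 12 on. The nonadjuster column pools three kinds of subject:

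- those who stayed at or above PASI75;
- those who met the criterion but were left on 160mg;
- those who left the study without adjusting, including withdrawals below PASI50.

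No table separates them. A difference between the columns would therefore appear even if the two doses worked equally well, and a reader of the study report could take it for an effect of the increase. The table named as the main look at this question cannot answer it.

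**Working it through.** The plan states no effect size, power or expected difference for this comparison, so there is no figure to reproduce. The check is whether the planned grouping creates a difference when the dose has no effect.

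**Inputs from the documents.** Visits every 4 weeks to Week 48; from Week 12, improvement of 50% to <75% makes a subject eligible for increase, and improvement below 50% leads to withdrawal; nonadjusters are all who are never increased; summaries by observed cases, LOCF and NRI.

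**Assumed, because the documents give no response rates.** Improvement = 1 − exp(b + e), where b is a lasting subject effect and e is visit noise. Median improvement was 70–90%, the SD of b was 0–1.2, and the SD of e was 0.4–0.6. A subject eligible at any visit from Week 12 to Week 44 was increased with probability 1 or 0.5. There were 200,000 subjects per scenario and the effect of 320mg was zero.

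**Results, adjusters / nonadjusters, increase probability 1 (%):**

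| Median improvement; SD of b; SD of e | Observed mean improvement, Wk 24 | Observed mean improvement, Wk 48 | LOCF mean, Wk 48 | PASI50 NRI, Wk 48 | PASI75 NRI, Wk 48 |
|---|---|---|---|---|---|
| 90; 0.4; 0.6 | 83.4 / 90.5 | 84.9 / 90.0 | 79.6 / 85.6 | 87.9 / 91.6 | 77.2 / 87.7 |
| 90; 1.2; 0.4 | 75.3 / 93.4 | 78.7 / 93.4 | 64.0 / 78.0 | 65.7 / 84.5 | 48.3 / 83.6 |
| 80; 0.8; 0.4 | 74.4 / 90.0 | 77.9 / 89.8 | 62.3 / 64.5 | 62.6 / 66.0 | 44.2 / 64.1 |
| 70; 0.8; 0.4 | 72.4 / 88.8 | 76.7 / 88.7 | 57.0 / 34.6 | 53.3 / 36.5 | 35.7 / 35.0 |
| 80; 0; 0.6 | 76.5 / 71.0 | 76.0 / 76.0 | 61.5 / 37.4 | 62.1 / 9.3 | 42.5 / 6.5 |

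**Observed data after Week 12.** In all 8 scenarios with lasting subject differences (SD of b above 0), adjusters were lower at Weeks 24 and 48. The smallest gap is 90.0 − 84.9 = 5.1 points and the largest 93.4 − 75.3 = 18.1 points. With no lasting differences (last row) the Week 48 gap is zero.

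**Other tables.** PASI50 at Week 12 favoured adjusters in every scenario (100% against 40.7–97.7%), because a subject must stay at or above PASI50 to remain available for increase. The 70% row has 28.6% of subjects below PASI50 at Week 12. There, LOCF and PASI50 NRI at Week 48 favour adjusters and PASI75 NRI is level. The 80% row with lasting differences has 15.3% below PASI50 at Week 12, and its LOCF means are close.

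**Choice of comparator.** A second zero-effect model used a log residual PASI with subject mean −1.2 to −2.3 and SD 0.9, and visit noise with SD 0.45 and lag correlation 0.5. Since exp(−1.2) = 0.30 and exp(−2.3) = 0.10, median improvement runs from 70% to 90%. The decision was taken afresh at each qualifying visit (probability 0.5).

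- At mean −1.2, Week 48 PASI50 NRI was 54% in adjusters and 41% in nonadjusters; PASI75 NRI was only 4 points lower in adjusters.
- Qualifiers never increased still beat adjusters by about 3–10 points on Week 48 PASI75, and by 17 points if lower responders were preferentially increased. That group is defined by its future: some members rebounded and so were no longer eligible.
- Grouping qualifiers by the decision at the first qualifying visit brought the two groups within 1 point when the decision was random. About 8 points remained when lower responders were preferred.

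**The case against.** The analysis is descriptive: no hypothesis is tested and no error rate is affected. The secondary objective on dose increase concerns safety and tolerability, and the efficacy objective concerns 160mg. Protocol 14.5 sets its purpose for the efficacy summaries together, and other outputs bear on it. SAP 8.2.1 re-baselines PASI at the start of 320mg, SAP 10 plots individual PASI with the timing and dose of each administration, and SAP 3.1 flags dose switches in listings. With up to 45 subjects, any refined comparator will be small, and SAP 3.1 leaves the mean blank at n of 3 or fewer.

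This limits the harm to interpretation, and the point about small groups stands. The other outputs do not repair the comparison. The re-baselined summary has no comparator and starts at a visit selected for low response, so regression to the mean can look like benefit. Protocol 14.5 confined it to single adjusters, whereas SAP 8.2.1 applies it to adjusters, now a combined group, so it may include visits after return to 160mg. SAP 8.2 still names the adjustment-category summary as primary and gives no caution on reading it.

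A reader might infer more than the documents support:

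- **That adjusters must look worse in every PASI table.** Withdrawals below PASI50 without adjustment count as nonadjusters, and SAP 4.2 expects discontinuation to cause missing data in many cases. This can level or reverse PASI50, LOCF and NRI results.
- **That a useful 320mg dose would look harmful.** Only a zero dose effect was simulated.
- **That qualifiers never increased are a like-for-like control.** They are not, as shown above.

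**Conclusion.** The concern holds as a matter of confounding, not of fixed direction. Subjects are classified by their own post-baseline PASI and then compared on PASI, so the adjuster versus nonadjuster tables cannot show the impact of dose adjustment. With no dose effect and lasting differences between subjects, adjusters will usually look worse in observed data after Week 12, by about 5 to 18 points of mean improvement. LOCF, NRI and PASI50 results can go either way. The sizes depend on assumed response rates, variability and increase probabilities. The classification problem follows from the documents alone and does not depend on which wording of the increase criterion applies.

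**What to change.** 1. In SAP 8.2 and 8.2.1, add a PASI display limited to subjects who met the increase criterion while on 160mg. Count time from the first qualifying visit. Compare those increased at that visit with those not increased at that visit, whatever happened later, and show PASI at that visit for both. Pool the PS0016 arms, and use individual profiles if a group is small.
2. In the existing tables, show never-qualified nonadjusters separately, with withdrawals below PASI50 identified.
3. State in the SAP that adjuster versus nonadjuster differences reflect selection on response and are not estimates of a dose effect. This sentence is worth adding even if nothing else changes.
4. Reconcile the increase criterion in Protocol 5.1 and Table 5–1 with that in Protocol 7.2, since it defines who qualifies. Correct the pointer in SAP 8.2 to Section 4.10, which reads as not applicable; the categories are in 3.6.

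Cost: SAP wording, a few derived flags from PASI, dosing and disposition data already collected, and one added display. Groups would average roughly 3–17 subjects under the assumptions used. Some subjects not increased at first will be increased later, which would dilute any real difference. Confounding by Investigator discretion remains, so the new display is a closer comparison, not an unbiased one.
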